4.2 Secondary Endpoints

- **Bipolar Voltage Correlation:** Statistical correlation and evaluation of systematic bias (limits of agreement) between the bipolar voltage amplitudes recorded by the two catheters in matched anatomical regions.
- **Multipolar Voltage Correlation:** Statistical correlation and evaluation of systematic bias (limits of agreement) between the multipolar voltage amplitudes recorded by the Optrell catheter and the bipolar voltage amplitudes recorded by the Octaray catheter in matched anatomical regions
- **Clinical Efficacy:** Freedom from any documented atrial tachyarrhythmia lasting ≥ 30 seconds at 1, 3, 6, 9, and 12 months.
- **Safety:** Incidence of acute procedural complications prior to hospital discharge.

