3.2 Secondary Objectives

- To perform a paired comparison of bipolar voltage amplitude distributions in the left atrium recorded by the Optrell versus the Octaray catheter during CS pacing before and after ablation.
- To perform a paired comparison of multipolar voltage amplitude distributions in the left atrium recorded by the Optrell versus bipolar voltage with the Octaray catheter during CS pacing before and after ablation.
- To evaluate the safety profile of the dual-catheter mapping approach.
- To assess long-term clinical outcomes, specifically the 12-month freedom from recurrent atrial tachyarrhythmias (AF, atrial flutter, or atrial tachycardia).

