7. FOLLOW-UP

7.1 Acute Safety Follow-Up

Because the investigational component of this study consists solely of additional electrophysiological mapping time using commercially approved technologies within a standard-of-care procedure, an independent Data Safety Monitoring Board (DSMB) will not be established. Instead, a designated Medical Monitor will oversee safety reporting throughout the study.

The Medical Monitor will be a senior cardiologist with expertise in cardiac procedures who is not involved in the conduct of the study and has no direct role in patient enrollment, procedures, or data analysis. The Medical Monitor will independently review all reported safety events.

All acute procedural complications and safety events will be reviewed by the Medical Monitor within 72 hours of notification.

Adverse Event (AE) and Serious Adverse Event (SAE) forms will be completed by the research coordinator in collaboration with the procedural operator and documented in the study Case Report Form (CRF; Appendix C).

If serious adverse events directly attributable to the repolarization mapping protocol occur in ≥ 2 of the first 10 enrolled patients, study enrollment will be temporarily paused, and an ad-hoc safety review will be conducted by the Medical Monitor and study leadership to determine whether protocol modification or study termination is necessary.

Definitions

AE

An AE is any unfavorable and unintended medical occurrence in a study participant undergoing the procedure, whether or not it is considered related to the study protocol.

CONFIDENTIAL

166 **SAE**

167 An SAE is any adverse event that results in one or more of the following outcomes:

- 168 • Death
- 169 • Life-threatening event
- 170 • Stroke/TIA
- 171 • Persistent or significant disability or incapacity
- 172 • Unplanned hospitalization or prolongation of hospitalization
- 173 • Any important medical event that may jeopardize the patient or require medical or surgical
- 174 intervention to prevent one of the outcomes listed above

175
176 For the purposes of this study, the following procedural complications will be classified and
177 reported as SAEs:

- 178 • Pericardial effusion or cardiac tamponade
- 179 • Stroke/TIA
- 180 • Phrenic nerve injury
- 181 • Vascular access complications requiring intervention
- 182 • Esophageal injury
- 183 • Heart failure exacerbation requiring treatment
- 184 • Prolonged hospitalization (>24 hours beyond the expected post-procedural course)

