- 185 • Any other serious adverse event related to the procedure

186

187 **Safety Follow-Up Period**

188 Formal protocol-mandated safety follow-up will extend through 7 days after the procedure or until
189 hospital discharge, whichever occurs later.

190 All AEs and SAEs occurring during this period will be documented in the CRF and reviewed by
191 the Medical Monitor.

192

193 **7.2 Clinical Follow-Up and Rhythm Monitoring**

194 Patients will undergo highly structured longitudinal follow-up to monitor for clinical and
195 subclinical arrhythmia recurrence and symptom status.

196 **Clinic Visits:**

CONFIDENTIAL

Patients will be evaluated at the following time points after the ablation procedure:

- 1 month \pm 14 days
- 3 months \pm 30 days
- 6 months \pm 30 days
- 9 months \pm 30 days
- 12 months \pm 30 days

Visits at 3 and 12 months will be conducted in person, while other visits may be conducted in person or via telemedicine, depending on clinical circumstances.

During these visits, the following information will be collected:

- Symptoms suggestive of arrhythmia recurrence
- Medication use, including antiarrhythmic drugs and anticoagulation
- Interval hospitalizations or cardiovascular events
- Standard ECG documentation when available

Rhythm Monitoring:

To systematically detect symptomatic and asymptomatic arrhythmia recurrence, patients will undergo scheduled ambulatory rhythm monitoring during follow-up.

A minimum of three 48-hour Holter monitors will be performed at:

- 3 months \pm 30 days
- 6 months \pm 30 days
- 12 months \pm 30 days

Additional rhythm monitoring (Holter, event monitor, or ECG) may be performed at the treating physician's discretion if symptoms suggest arrhythmia recurrence.

Recurrence of atrial arrhythmia will be defined as documented AF or atrial tachycardia lasting \geq 30 seconds after the standard 2-month blanking period.

Community-Based Testing: To facilitate protocol compliance, both the 12-lead ECGs and the 24-hour Holter monitors may be performed locally at the patient's primary care clinic (Kupat Holim). The study coordinator is responsible for retrieving and analyzing these community-based reports and logging the data into the study database.

228

229 **7.3 Post-Procedure Antiarrhythmic Drug Management**

230 The use of AADs following the ablation procedure will be at the discretion of the treating
231 electrophysiologist and managing physician, in accordance with routine clinical practice.

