Optrell bipolar	 Yes  No	 Yes  No	_____ points
Optrell multipolar	 Yes  No	 Yes  No	_____ points

SECTION 3: PHASE 2 - ABLATION DETAILS

Variable	Data Entry
Ablation Energy Used	 RFA  PFA
PVI Performed?	 Yes  No
PVI Successfully Achieved?	 Yes  No
First Pass Isolation ?	 Yes  No
Linear Lesions Created (Check all that apply)	 Roof Line  Posterior Wall Isolation (PWI)  Cavotricuspid Isthmus (CTI)  Mitral Isthmus Line  Other: _____

SECTION 4: PHASE 3 - CONDUCTION BLOCK ASSESSMENT

(Complete this sub-section for EVERY linear lesion created. See Section 4b, 4c and 4d. Duplicate if necessary.)

Line Checked	 Roof Line  Posterior Wall Isolation (PWI)  Cavotricuspid Isthmus (CTI)  Mitral Isthmus Line  Other:	
Ablation Energy Used	 RFA  PFA	

Assessment Method	Time to Verify Block	Block Confirmed?
Optrell Vector Assessment (time to assess block by moving the catheter across the line to review vectors)	___ min : ___ sec	 Yes  No
Octaray Activation Mapping (time to create an activation map sufficient to determine presence or absence of block)	___ min : ___ sec	 Yes  No

Concordance for this line: ☐Yes (Methods agree) ☐No (Methods disagree)

Explain:_____

SECTION 5: ACUTE PROCEDURAL COMPLICATIONS (completed at hospital discharge)

Variable	Data Entry
None	
Pericardial Effusion / Tamponnade	
Stroke / TIA	

CONFIDENTIAL

Variable	Data Entry
Vascular Complication requiring intervention	
Phrenic Nerve Injury	
Prolongation of Hospitalization (>24 hours beyond the expected post-procedural course)	
Esophageal injury	

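### The only safety endpoint stops at hospital discharge, although the protocol's own acute safety period runs to day 7 or discharge, whichever is later

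*Protocol*

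**What the plan says.** Protocol section 3.2 lists a safety objective: "To evaluate the safety profile of the dual-catheter mapping approach". Section 4.2 gives one endpoint for it, "Incidence of acute procedural complications prior to hospital discharge", and section 4 contains no other safety endpoint. The complication page of the procedural CRF (Appendix D, Section 5) follows the same cut-off; it is headed "ACUTE PROCEDURAL COMPLICATIONS (completed at hospital discharge". The redo CRF in Appendix F carries the same heading.

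Section 7.1 sets a different period: "Formal protocol-mandated safety follow-up will extend through 7 days after the procedure or until" "hospital discharge, whichever occurs later". It continues: "All AEs and SAEs occurring during this period will be documented in the CRF and reviewed by" the Medical Monitor. Its SAE criteria include "Unplanned hospitalization or prolongation of hospitalization", and its list of procedural complications to be reported as SAEs closes with "Any other serious adverse event related to the procedure".

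**The concern.** The protocol has two windows for acute safety, and no text reconciles them. An event can meet the 7.1 definition of a procedural complication, fall inside the 7.1 period, and still be excluded from the only endpoint that answers the safety objective. An example is a procedure-related readmission on day 4 in a patient discharged on day 1. The same applies to a post-discharge event that the investigator marks on the Appendix C form as possibly related to the mapping protocol, which is the exposure the objective is about.

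What is at stake is the headline complication rate. It leaves out part of the period the protocol itself treats as acute, so it is not a conservative figure. The cut-off is also each patient's own discharge date, so patients are observed for different lengths of time. A complication that prolongs the stay lengthens that patient's window, while an uneventful early discharge shortens it.

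**Working it through.** The protocol states no safety calculation, so there is no figure to reproduce. The check is a comparison of the two windows, followed by arithmetic to show scale.

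**Windows compared**

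| | Start | End |
|---|---|---|
| Endpoint (4.2; Appendices D and F complication pages) | procedure | discharge |
| Acute safety follow-up (7.1) | procedure | later of day 7 and discharge |

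The two coincide only when discharge falls on day 7 or later. For discharge on day *d* < 7, the interval from *d* to day 7 is monitored but not counted.

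**Inputs**
- Number of patients: 30 (section 8.1).
- Discharge day: not stated. Assumed to be day 1, 2 or 3.
- Per-patient chance *p* of a procedural complication between discharge and day 7: not stated. Assumed to be 1%, 2% or 3%.

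**Share of the 7 days outside the endpoint**, (7 − *d*)/7:
- *d* = 1: 6/7 = 86%
- *d* = 2: 5/7 = 71%
- *d* = 3: 4/7 = 57%

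These are shares of time, not of risk. Nothing in the protocol says how risk is spread over the week.

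**Chance that at least one of 30 patients has an uncounted complication**, 1 − (1 − *p*)^30, taking patients as independent:
- *p* = 0.01: 1 − 0.99^30 = 26.0%
- *p* = 0.02: 1 − 0.98^30 = 45.5%
- *p* = 0.03: 1 − 0.97^30 = 59.9%

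**Effect of one such patient on the reported incidence.** If that patient had no earlier complication, the numerator falls by one, and 1/30 = 3.3 percentage points. With exact (Clopper-Pearson) two-sided 95% intervals:

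| Counted under 4.2 | Counted under the 7.1 period |
|---|---|
| 0/30 = 0% (0 to 11.6%) | 1/30 = 3.3% (0.1 to 17.2%) |
| 2/30 = 6.7% (0.8 to 22.1%) | 3/30 = 10.0% (2.1 to 26.5%) |

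The first row matters most in practice: with 30 patients, one post-discharge event decides whether the study reports no complications or one.

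**The case against.** The strongest reply is that the two sections do different jobs. Section 4.2 says what is summarised; 7.1 says how long events are collected and reviewed. Collecting for longer than the endpoint window is ordinary, and Appendix B schedules adverse event assessment out to 12 months without anyone expecting all of it in the endpoint. The endpoint also agrees with the complication pages in Appendices D and F, which looks like a deliberate in-hospital definition. Ascertainment before discharge is more reliable, since Appendix B schedules no contact between discharge and the 1-month visit. Later events still reach the Medical Monitor and could be tabulated in an analysis plan that is not shown.

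Much of this is fair. A narrower endpoint can be legitimate, the later events are not lost to oversight, and the magnitudes above rest on assumed inputs. The exact intervals in each pair overlap heavily, and no test uses this endpoint. The enrolment pause rule in 7.1 and section 10 counts adverse events directly and is unaffected. A patient-specific cut-off would also remain under the 7.1 period for stays beyond day 7, although every patient would then have a window of at least 7 days.

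What does not stand is that this is only a difference between collection and reporting. The 12-month assessments are routine visits. The 7-day period is what the protocol itself presents as acute safety follow-up, and its list of procedural complications carries no discharge limit. The endpoint counts acute procedural complications, so one term has two windows and no reason is given for the shorter one. An analysis plan could add a table, but the endpoint definition is fixed in the protocol.

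**Conclusion.** The concern holds, as a minor point. As written, section 4.2 excludes from the only safety endpoint any procedural complication between discharge and day 7, although 7.1 requires it to be collected and reviewed. The reported incidence can equal the rate over the protocol's acute period or fall below it, never exceed it. Each affected patient with no earlier complication costs 3.3 percentage points of 30. The chance that at least one patient has such an event is 26.0% to 59.9% for assumed per-patient risks of 1% to 3%. The protocol supports neither those risks nor any discharge day, so these figures indicate scale only. If no complication follows discharge, or nobody leaves before day 7, the two rates are identical. No primary endpoint changes.

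**What to change.** In section 4.2, define the safety endpoint as the proportion of patients with at least one procedural complication from the 7.1 list, through 7 days after the procedure or hospital discharge, whichever is later. Report the pre-discharge count as a sub-line, so the in-hospital figure stays available. Either complete the complication pages in Appendices D and F at the end of that period, or derive the endpoint from the Appendix C forms, which already serve the same period.

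The cost is one phrase in 4.2 and one heading in each of Appendices D and F. No data are needed beyond what 7.1 already mandates. The downside is that events after discharge depend on patient contact or outside records, and Appendix B has no contact before the 1-month visit. That visit already includes an adverse event assessment, and its 14-day window still places it after day 7, so asking there about the first 7 days would meet the need without an extra contact. A day-7 telephone call would give more timely capture but is optional.

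If an in-hospital endpoint is intended, section 4.2 should say so, give the reason, and state that complications through day 7 will be reported beside it.

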5. STUDY POPULATION

The study will enroll a cohort of patients in whom the likelihood for needing ablation lines beyond PVI is high.

5.1 Inclusion Criteria

- Age ≥ 18 years.
- Documented persistent atrial fibrillation and/or atrial flutter.
- Undergoing a clinically indicated first-time (de novo) or redo catheter ablation where linear ablation lesion sets (e.g., posterior wall, roof line, lateral mitral line, CTI) are planned or anticipated.
- Ability to provide written informed consent.

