5.2 Exclusion Criteria

- Paroxysmal or persistent AF where only standard PVI is planned.
- Mechanical mitral valve
- Presence of intracardiac thrombus or contraindication to systemic anticoagulation
- Any medical condition or anatomical contraindication that, in the investigator's judgment, precludes safe participation.
- Pregnant women
- Ability and willingness to provide written informed consent.

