6.2 Intra-Procedural Workflow

The procedure will be performed under general anesthesia. Following standard venous access, transseptal puncture will be performed to access the left atrium. Systemic anticoagulation with intravenous Heparin will be administered and maintained to achieve an activated clotting time (ACT) >300 seconds.

• Phase 1: Voltage Mapping (coronary sinus pacing)

Following transseptal access and prior to ablation, a left atrial 3D map using TPI with left atrial voltage mapping will be performed using the Octaray catheter. The Octaray catheter will then be exchanged for the Optrell catheter, and a second high-density voltage map will be acquired on the

same 3D map (remap). A high density Multipolar map using parallel mapping will be performed in the same time with the Optrell catheter. All the maps need to have a fill threshold $\leq 3\text{mm}$ to allow sufficient density.

For patient in atrial fibrillation, an electrical cardioversion will be performed and mapping will be performed during coronary sinus pacing. For patient in sinus rhythm, mapping will be performed during coronary sinus pacing. For patient in atrial flutter, mapping will be performed in arrhythmia.

• **Phase 2: Ablation:**

The operator will perform PVI and any clinically indicated linear lesion sets according to standard of care using either radiofrequency or pulsed field ablation energy.

• **Phase 3: Conduction Block Assessment**

After completing the ablation phase, conduction block across lines will be assessed using both methods:

- *Optrell Vector Assessment*: Real-time evaluation of conduction vectors using the Optrell catheter and V8 software. The time to determination, from the beginning of the mapping (pacing start) to block confirmation, and the binary result (block vs. no block) will be recorded.
- *Standard Activation Mapping*: Creation of a full activation map using the Octaray catheter (often requiring pacing maneuvers) to establish the gold-standard confirmation of block. Time to determination, from the beginning of the mapping to block confirmation, and the binary result will be recorded.

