6.3 Distinction Between Research Protocol and Clinical Standard of Care

It is important to emphasize that patients enrolled in this study will undergo the same clinically indicated ablation procedure and receive the same standard of care as non-participating patients. The sole distinction for research participants is the inclusion of the two additional mapping sequences: one performed prior to ablation (for the paired voltage amplitude comparison) and one performed after ablation (for the comparative conduction block assessment). Furthermore, all mapping and ablation technologies utilized during these additional research steps, including the Optrell and Octaray catheters, as well as their respective 3D mapping systems and software, are

fully approved for clinical use by the FDA, CE, and AMAR, and are routinely employed in standard clinical practice at our institution.

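### A flutter patient with only a right-atrial CTI line planned is eligible, yet the workflow prescribes transseptal puncture and two left atrial maps, contrary to the protocol's own standard-of-care and risk statements

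*Protocol*

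**What the plan says.** Eligibility is set by two bullets of Protocol section 5.1. The rhythm criterion is "Documented persistent atrial fibrillation and/or atrial flutter", so flutter alone is enough. The lesion criterion covers a first or repeat ablation where "linear ablation lesion sets (e.g., posterior wall, roof line, lateral mitral line, CTI) are planned or anticipated". CTI is one of the four lines named, and neither PVI nor a left atrial line has to accompany it. The nearest exclusion in 5.2 is "Paroxysmal or persistent AF where only standard PVI is planned", which concerns AF patients only.

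The workflow in section 6.2 says that "transseptal puncture will be performed to access the left atrium". Phase 1 continues: "Following transseptal access and prior to ablation, a left atrial 3D map using TPI with left atrial voltage mapping will be performed" with Octaray. That catheter is then exchanged for Optrell and the chamber is mapped again. The one provision for flutter is "For patient in atrial flutter, mapping will be performed in arrhythmia". Section 7.4 repeats the left atrial maps at any redo within 12 months.

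Section 6.3 describes the research component: "The sole distinction for research participants is the inclusion of the two additional mapping sequences". Section 9.2 assumes an AF ablation, gives roughly 15 minutes of prolongation as the main study-specific risk, and attributes tamponade and stroke or TIA to the standard procedure.

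**The concern.** The criteria admit a patient for whom the prescribed workflow goes beyond that patient's own treatment. A CTI-only flutter ablation is a right atrial procedure. If 6.2 is followed, this patient has the septum crossed and the left atrium mapped twice for research purposes alone.

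The first issue is patient safety. The risk section treats the complications of left atrial access as risks the patient would run anyway, which is not so here. The consent counselling listed in 9.3 does not mention study-driven left atrial access. Sections 7.1 and 10 also justify having no data safety monitoring board on the premise that the study adds nothing but mapping.

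The second issue is data. If the operator sensibly leaves out the left atrial steps, the patient departs from 6.2 and gives no pair for the objective of comparing "bipolar voltage amplitude distributions in the left atrium recorded by the Optrell versus the Octaray catheter".

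**Working it through.** The protocol states no figure to reproduce. The check follows one hypothetical patient through the text: documented atrial flutter, no AF, and a CTI line as the only planned lesion.

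| Step | Protocol section | Result for this patient |
|---|---|---|
| Rhythm criterion | 5.1, second bullet | Met: flutter alone suffices |
| Lesion criterion | 5.1, third bullet | Met: CTI is named and no second lesion is required |
| PVI-only exclusion | 5.2, first bullet | Does not apply: it concerns AF, and no bullet covers flutter with CTI only |
| Investigator-judgment exclusion | 5.2 | Does not apply: lacking a left atrial target is neither a medical condition nor an anatomical contraindication |
| Left atrial access | 6.2, opening paragraph | Prescribed, no condition |
| Left atrial maps | 6.2, Phase 1 | Prescribed with both catheters, no condition |
| Flutter provision | 6.2, Phase 1 | Changes the rhythm during mapping, not the chamber or the access |
| Redo within 12 months | 7.4 | Left atrial maps prescribed again, no condition |
| Research versus care | 6.3 | Only mapping is said to differ; not true for this patient |
| Study-specific risk | 9.2 | Only added time is named; not true for this patient |

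Counts per affected patient, as written:

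- Transseptal punctures at the index procedure: 1.
- Left atrial catheter maps at the index procedure: 2 (Octaray, then Optrell, whose multipolar map is acquired at the same time).
- Left atrial catheter maps if a redo is done: 2 + 2 = 4 in total.

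If the left atrial steps are omitted instead, each such patient removes 1/30 = 3.3% of the target sample from the left atrial voltage comparison. Nothing is lost from the primary endpoints of concordance and time, which are assessed per line. Paired right atrial voltage data also remain possible: the voltage endpoints in 4.2 refer to matched regions without naming a chamber, and the procedural CRF has right atrial map rows.

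The number of such patients is not given. Sections 5.1 and 5.2 set no limit, so any number from 0 to 30 is compatible with the protocol, and no share is assumed here.

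**The case against.** The strongest reply is that the protocol has a narrower patient in mind. The synopsis speaks of complex atrial arrhythmias. Section 2.1 and the opening of section 5 present the lines, CTI among them, as additions to PVI, and 9.2 refers to an AF ablation. On that reading CTI is an extra line within a left atrial procedure, 6.2 merely describes the procedure these patients are already having, and 6.3 would itself bar a puncture that is not indicated. Phase 2 of 6.2 mentions PVI, which would need left atrial access in any case. The CRF asks whether each left atrial map was completed, so it can record a patient without one. Finally, 9.2 calls the prolongation the primary risk rather than the only one, and it does list tamponade and stroke or TIA.

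Part of this stands. The probable intent is that enrolled patients have left atrial access for their own treatment, and nothing shows that CTI-only patients are sought. The reply does not close the gap, however:

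- None of the scope statements is an eligibility criterion, while 5.1 expressly admits flutter without AF.
- Section 6.3 describes what the study adds. It does not instruct the operator to omit a step that 6.2 prescribes.
- The Yes/No fields in the CRF record what happened and do not make a prescribed step optional.
- PVI in Phase 2 is reasonably read as following standard of care. If it were compulsory, a CTI-only patient would receive a protocol-driven PVI, which conflicts with 6.3 more seriously.
- Added time is still the only risk that 9.2 names as specific to the study. The listed complications are attributed to the standard procedure.

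**Conclusion.** The concern holds and should be fixed. Followed as written, the protocol gives an eligible CTI-only flutter patient 1 transseptal puncture and 2 left atrial catheter maps that the patient's treatment does not call for, and 2 further left atrial maps at a redo. Sections 6.3 and 9.2 are then untrue for that patient.

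The conclusion rests on two things the protocol does not state: that the CTI is a right atrial structure, which is basic anatomy, and that a CTI-only ablation has no other reason to enter the left atrium. The number of patients affected is unknown and may be zero, which is why this is not rated higher. The per-line primary endpoints are not at risk. The loss to the left atrial voltage comparison, if operators omit the steps, is 3.3% of the target sample per patient.

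**What to change.** Preferred: extend the third bullet of 5.1 with a clause such as *and where left atrial access is part of the clinically indicated procedure, independent of the study*. CTI then remains a study line within such procedures, and 6.2, 6.3 and 9.2 hold on this point for everyone enrolled. The cost is one clause by amendment and perhaps slightly slower recruitment.

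Alternative, if the sponsor wants to keep CTI-only patients: state in 6.2 and in 7.4 that the transseptal and left atrial mapping steps apply only when left atrial access is clinically indicated. State also that CTI-only patients contribute to block concordance and time but not to the left atrial voltage objectives in 3.2. The cost is one sentence in each section and a few patients without left atrial voltage pairs.

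Which patients need left atrial access is for the investigators to judge.
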